The purpose of the study is to examine whether ACT can be an effective intervention in increasing quality of life in older adults (aged 65+), presenting to older adult mental health service with psychological difficulties, as well as why ACT is effective.

PRIMARY OBJECTIVE

In this study we aim to investigate the efficacy of ACT for supporting older adult clients experiencing psychological distress.

SECONDARY OBJECTIVE(S)

In addressing the primary objective, we will be guided by three fundamental questions: (1) Do (meaningful) changes occur for client-participants over the course of ACT intervention? (2) Are observed changes broadly attributable to the ACT intervention? (3) What specific factors (ACT-specific, non-specific, extra-therapeutic) contribute to observed changes?

The study will also identify adaptations that may be facilitative of change when using ACT with older adult clients, **with consideration of the impact that moving the study to a telephone/videocall delivered intervention.**

OUTCOME MEASURES

PRIMARY OUTCOME MEASURE

1. Change in quality of life assessed using the Older People's Quality of Life questionnaire (OPQOL-brief; Bowling, Hankins, Windle, Bilotta, & Grant, 2013). Completed by participant.

SECONDARY OUTCOMES

Symptom measures

1. Client's level of cognitive functioning assessed using the Montreal Cognitive Assessment (MoCA; Nasreddine et al., 2005). Completed by MHSOP team with the participant.
2. Changes in symptoms of anxiety and depression assessed with the Hospital Anxiety and Depression Scale (HADS; Zigmond & Snaith, 1983). Completed by the participant.

Change measures

1. Change in/progress on client's goals assessed using the Simplified Personal Questionnaire (PQ; Elliot, Mack, & Shapiro, 1999). Completed by participant with guidance from therapist.
2. Client's attribution of change and view on therapy assessed with the Change Interview (Elliott, Slatick, & Urman, 2001). Conducted by secondary researcher with participant.

Process measures

1. Change in psychological flexibility assessed using the CompACT-8 (Morris, Dawson, & Golijani-Moghaddam, 2019). Completed by participant.

Session measures

1. Change in client's weekly level of quality of life assessed using the Outcome Rating Scale (ORS; Miller, Duncan, Brown, Sparks & Claud, 2003). Completed by participant.
2. Change in therapeutic alliance assessed with the Session Rating Scale (SRS; Duncan et al., 2003). Completed by participant.

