3. Client's (qualitative) views on individual therapy sessions assessed with the Helpful Aspects of Therapy form (HAT; Lewlyn, Elliott, Shapiro, Firth, & Hardy, 1988). Completed by therapist in discussion with participant.

Fidelity measure

1. Adherence to ACT related processes assessed with the ACT Fidelity Measure (ACT-FM; O'Neill, Latchford, McCracken & Graham, 2019). Completed by therapist and secondary researcher.

EXPLORATORY OUTCOMES

Adaptations made to treatment will be recorded so that commentary can be made on what adaptations to ACT may be beneficial for older adult clients. **Consideration of the impact that delivering the intervention in a remote manner will also be made and any adaptations that were made to facilitate this.**

TABLE OF OUTCOMES

Objectives	Outcome Measures	Timepoint(s) of evaluation of this outcome measure (if applicable)
Primary Objectives	1. Quality of life (OPQOL-brief).	1. Baselines, pre-, mid- and post-intervention, and at six-week follow up.
Secondary Objectives	Symptom measures 1. Cognitive functioning (MoCA). 2. Changes in levels of anxiety and depression (HADS).	1. At initial contact, by service as standard practice. 2. At initial contact, by service as standard practice. Baselines, pre-, mid- and post-intervention,

		and at six-week follow up.
	Change measures 
 1. Client's goals (PQ). 2. Client's view on change (Change Interview). 	
 1. Prior to each weekly treatment session. 2. One week after finishing treatment.
	Process measure 
 1. Psychological flexibility (CompACT-8). 	
 1. Baselines, pre-, mid- and post-intervention, and at six-week follow up.
	Session measures 
 1. Quality of life/general outcomes (ORS). 2. Therapeutic alliance (SRS). 3. Client's views on the therapy session (HAT). 	
 1-3. At the end of each weekly treatment session.
	Fidelity measures 
 1. Fidelity of treatment (ACT-FM). 	
 1. At the end of each session (by therapist) and random sampling of all sessions (by Secondary Research Supervisor).

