Exploratory/Tertiary Objectives	
 1. Beneficial adaptations for ACT. 2. Impact of telephone/videocall and adaptations to this. 	
 1. Noted throughout the study by researcher and commented on in final write up. 2. Noted throughout the study by researcher, factored into impact of results, and commented on in final write up.

STUDY DESIGN

To address the aims and sub-objectives listed previously, the study will employ an adjudicated Hermeneutic Single Case Efficacy Design (HSCED) series. Following Elliott's

(2002; Elliott et al., 2009) approach, the first step for a HSCED is the formation of rich case records. Developed for each client, these consist of data from various time points in the study, and include demographic, quantitative (outcome measures, treatment fidelity measures etc.) and qualitative sources (Change Interview, therapy feedback, therapy process notes and recordings). The rich case records are then cross-referenced and synthesised into an affirmative and sceptic brief. These briefs are then presented to an expert panel to be adjudicated on the process of change (see Figure 1).

[figure not shown]

Figure 1: the HSCED process (Stephen et al., 2011).

Affirmative brief

The purpose of the affirmative brief is to demonstrate direct links between the therapeutic intervention and outcomes, and is divided into three parts: 1) a brief of the main lines of argument for these links; 2) a rebuttal against the arguments made in the sceptic brief; and 3) a concluding summary narrative (Stephen et al., 2011). The affirmative brief draws evidence from five areas (see Table 1), with evidence in at least two areas required to warrant adjudication (Elliott, 2002).

Sceptic brief

The opposing sceptic brief demonstrates possible nontherapy processes which could account for change (Table 2), and uses the same structure of a brief, a rebuttal, and a narrative summary. Elliott (2002) talks about the sceptic brief being developed in a manner of good-faith to determine what non-therapy effects may have led to change.

DATA ANALYSIS

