To facilitate the cross-referencing of rich case records, several methods of analysis will be employed, dependent on the evidence area required for the affirmative or sceptic brief. These are outlined in Tables 1 and 2, respectively. All analyses will be completed using SPSS (Version 25.0; IBM Corp, 2017) or Microsoft Excel (Version 15.0.5179.1000; Microsoft Corporation, 2013). Analyses will be performed by the student researcher/therapist either at the MHSOP or the Universities of Lincoln or Nottingham. No data containing confidential information will be analysed outside of the MHSOP, in line with relevant NHS Trust policies.

Table 1		
Direct evidence for links between therapy process and outcome, from Elliott (2002).		
Direct evidence area	Description	Method of evaluation (specific analysis method)
1. Retrospective attribution	Change attributed by client to the therapy	Content of Change Interview (Framework Analysis)
2. Process-outcome mapping	Content of post-therapy changes correspond to specific processes within therapy	Correlations between within therapy measures (HAT), and quantitative outcome measures (Pearson correlation, or Spearman correlation if assumptions of normal distribution not met).
3. Within-therapy process-outcome correlation	In-therapy process variables covary with week-to-week changes in client problems	Correlations between ACT adherence and ORS, and the change questionnaire (i.e. the SPQ; Pearson/Spearman correlation)
4. Early change in stable problems	Therapy coincides with changes in long-standing client problems	Change in outcome measures from baseline to initial sessions (Pearson/Spearman correlation, visual analysis)
5. Event-shift sequences	Important events precede stable shifts in client problems, especially if therapy process and client change are logically related	Correspondence between within therapy measure (HAT) and variation in patient's problem (SPQ; Pearson/Spearman correlation, visual analysis)

Note: HAT – Helpful Aspects of Therapy form. SPQ – Simplified Personal Questionnaire.

Table 2

Evidence for links between nontherapy processes and outcome, from Elliott (2002)

Nonchange/ nontherapy area	Changes are...	Method of evaluation (analysis method)
1. Non-improvement	Either trivial or negative.	Assess reliable and clinical significance on measures (RCI calculations); ask ppt the importance and direction of any change (Change Interview).

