Therapy will use the above protocol as a guide for treatment; however, duration and content will be adapted based on the individual. Primarily this will be using extra sessions to focus on any content that participants may need further work with, but could also include a break in the middle of sessions. Sessions will predominantly be weekly and one hour in length, dependent on any required adaptations. Sessions will be delivered either over telephone or via QHealth. As ACT is a processes-based therapy, rather than a single manualised procedural treatment, adherence to a strict protocol is not theoretically mandated (Hayes & Hoffmann, 2017).

The basic structure of each session will be:

1. Participant completes weekly Personal Questionnaire before session.
2. Session begins with a mindfulness exercise.
3. Homework and concepts from previous session are reviewed.
4. New material for the session is covered.
5. Homework is assigned.
6. Therapist completed HAT with participant.
7. Participant is supported to complete ORS and SRS.

Following each session, the student researcher will receive clinical supervision with [name] by (secure) videocall or telephone to discuss any relevant case information, such as

risk and progress. A clinical note will be made on the participant's electronic case record, as in standard practice. The student researcher will also receive regular ACT supervision from [name], Secondary Research Supervisor/Chief Investigator to address any modality specific questions or dilemmas. Relevant discussions from this will be added to the participant's electronic case record as required.

At mid-point in therapy (usually session six), QP1.1 will be repeated at the start of the therapy session. QP1.1 will also be repeated at the final therapy session to act as the post-therapy time point.

During the final session, the PQ will be re-administered to determine whether there has been any change in their problem areas. Participants will also be given the opportunity to 're-author' their problem areas. This is to capture any theoretical change they may have occurred in identifying where problems at situation, as would be posited by the ACT theoretical framework (living with problems, rather than eliminating them). Participants will complete any required session questionnaires prior to filing in the PQ.

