The final session will also cover a summary of the sessions, as well as providing the participant with a therapy blueprint of what they specifically found useful. This will include any next steps for the participant (e.g. whether they will continue to be seen by the MHSOP) and what the process is for them to follow if there is a deterioration in mental health. The participant will be reminded of the data processing details and asked again if they would like a summary of the findings from the study.

One week after the final session, participants will complete a Change Interview, facilitated by [name], Trainee Clinical Psychologist, either face-to-face or by telephone/videocall, depending on the social distancing restrictions at the time. The Change Interview is a semi-structured interview to determine whether the client experienced change during the treatment, what they attributed this towards (e.g. therapeutic factors, external factors). The Change Interview is completed by a member of the research team the participant has not had previous contact with (to encourage more honest responses), and will be recorded on a NHS encrypted device so that the answers can be transcribed at a later date. The participants will then receive reimbursement towards their travel (if applicable) and for the factors of research which were additional to normal clinical treatment (extra questionnaires, attending Change Interview).

One month following the Change Interview, participants will be called up again by the Assistant Psychologist to complete QP 1.1. This will act as six-week post-therapy follow-up.

Following final therapy sessions, a secondary member of the research team (likely to be the Chief Investigator) will complete fidelity checks to ensure that the modality (ACT) is sufficiently adhered to. This will be conducted using a random sampling method and the researcher will have access to anonymised audio files, stored on an encrypted NHS Trust device.

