Should any of these criteria be met, the decision of whether the participant receives further support from the MHSOP will be decided by [name] and the wider MDT at the MHSOP. A replacement participant will be recruited, dependent of timeframe and ability to deliver therapy. Should criteria apply to all participants (such as evidence of the negative effects of ACT), the study as a whole will be temporarily stopped on ethical grounds. Interim analysis would be performed at this point to determine any negative effects of the intervention on the participants. Continuation of the study would be dependent on further guidance from the REC, NHS R&D and any other relevant parties.

ETHICAL AND REGULATORY CONSIDERATIONS

ASSESSMENT AND MANAGEMENT OF RISK

This study aims to reflect usual clinical practice where possible; therefore, the burden to participants will be of a similar level to treatment as usual. That is, they will be expected to attend one-to-one psychotherapy (either face-to-face or at distance) and to discuss their mental health difficulties; what contributed towards the development of their difficulties; and what is maintaining their difficulties. As with any psychological therapy, there is a potential risk that talking about distressing experiences will cause an increase in frequency or intensity of pre-existing mental health conditions.

These risks will be monitored through the study by the Trainee Clinical Psychologist (who is both researcher and therapist) through discussion with the participant, use of outcome measures and importantly by utilising weekly clinical supervision with [name] (Clinical Psychologist for the MHSOP). This allows a space for any concerns to be raised and for [name] to have clinical oversight of the participants. As part of standard clinical practice, and local NHS Trust policies, each participant will have a clinical risk assessment with the MHSOP. This will be reviewed by the researcher/therapist with [name] before starting therapy. Any relevant information will also be added to this, should anything relevant come up in therapy sessions.

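### For the exploratory outcome on beneficial ACT adaptations, the only source named is the notes and commentary of the researcher, who is also therapist and analyst; no client or independent source is linked to it

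*Combined protocol and SAP*

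**What the plan says.** Under Secondary Objective(s) the protocol states: "The study will also identify adaptations that may be facilitative of change when using ACT with older adult clients". The Exploratory Outcomes section gives the means: "Adaptations made to treatment will be recorded so that commentary can be made on what adaptations to ACT may be beneficial for older adult clients". The Table of Outcomes repeats this for the row on beneficial adaptations: "Noted throughout the study by researcher and commented on in final write up". The next row, on telephone or videocall delivery, is handled in much the same way.

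Adaptation is expected to be common. Under Therapeutic sessions, the session plan is only a guide and "duration and content will be adapted based on the individual".

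On roles, the Assessment and Management of Risk section describes one trainee as both researcher and therapist, and the Data Analysis section says "Analyses will be performed by the student researcher/therapist".

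The protocol also schedules an interview that this person does not conduct. One week after the last session, "The Change Interview is completed by a member of the research team the participant has not had previous contact with". Its purpose is described as follows: "The Change Interview is a semi-structured interview to determine whether the client experienced change during the treatment", together with what the client thinks caused that change.

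**The concern.** The objective goes beyond listing what was done: it asks which adaptations may have helped. The person named as the source for that answer delivers the adapted therapy, keeps the notes, runs the analyses and writes the commentary. A therapist's view of what helped is legitimate evidence, but it comes from someone with a stake in the answer.

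The protocol treats this kind of bias seriously elsewhere. It uses an unfamiliar interviewer so that clients will speak more frankly, it justifies the expert panel as a way to limit researcher bias, and Table 2 lists the wish to please the therapist or researcher as a rival explanation of change. None of these safeguards is tied to the adaptations outcome. At stake is how much weight a service could give to the study's statements about adapting ACT for older people or delivering it remotely.

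**Working it through.** No arithmetic applies. The check sets each source in the protocol against the adaptations outcome and asks whether the text links the two.

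| Source | Who supplies it | Linked in the text to adaptations? |
|---|---|---|
| Researcher's notes and commentary | Student researcher/therapist | Yes (Exploratory Outcomes; Table of Outcomes) |
| Notes of session content (Protocol Compliance) | Writer not stated | Not explicitly; intended for later analysis of process and change |
| HAT | Client's views, written down by the therapist with the client | No |
| Change Interview | Client, to an interviewer not met before | No; described as covering change, its causes and the view of therapy |
| ACT-FM | Therapist, plus a second team member on sampled sessions | No; measures adherence to ACT |
| Expert panel | Three Clinical Psychologists | No; asked whether change was substantial and what to attribute it to |

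One source is linked. No client-reported or independent source is.

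**Analysis tables.** Table 1 has five rows and Table 2 has eight, 13 in all; none mentions adaptations. The nearest are Table 1 row 5, which compares HAT entries with movement in the client's problems, and Table 2 row 3, which asks the client for good and bad accounts of the therapy. Either could pick up an adaptation, but neither is directed at one.

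**Panel.** Its three classes are ACT-specific, non-specific and extra-therapeutic. An adaptation such as extra sessions on one topic is part of the therapy it modifies, so this classification does not separate the two.

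**What weekly scores can add.** The Personal Questionnaire (PQ) is taken before each session and the Outcome Rating Scale (ORS) at the end of each. An adaptation that starts partway through therapy has earlier points to compare with, although it coincides with the session content of that week. One in place from session 1, as remote delivery is, has no earlier PQ or ORS point in the Table of Outcomes. For such adaptations the plots cannot help, and the client's own account is the most direct evidence available.

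**The case against.** The strongest reply is that client evidence is already within reach. The table entry sits in a column for timepoints and need not be a complete list of evidence. The Study Design section says in general terms that the single-case design serves all the aims, and its case records include the Change Interview, therapy feedback, process notes and recordings. The HAT gathers the client's view after every session. Protocol Compliance already provides for notes of session content, directly after saying that therapy may be adapted. The outcome is exploratory and cautiously worded.

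Much of this stands, and it rules out several stronger readings. A reader might infer that clients contribute nothing on adaptations, or that unhelpful ones could not come to light; the documents do not support this, since the HAT, the interview and the case records could all carry such views. A reader might infer that no client or panel question concerns adaptations; the interview schedule and the panel questionnaire are not in the documents, so that cannot be verified. A reader might infer that the therapist chose every adaptation; in fact, some, such as larger print, are settled at the referral assessment with the service's psychologist, and the choice of telephone or videocall follows the client's preference. Nor does the text set any rule by which the therapist's opinion alone makes an adaptation beneficial.

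What the reply does not supply is a commitment. The general design statement gives no route from case records to this outcome, the briefs built from those records argue therapy against non-therapy causes, and the HAT is filled in by the therapist.

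**Conclusion.** The point holds as a minor design improvement. The only named source for this outcome is the researcher's notes and commentary, and the documents link no client or independent source to it. It does not touch the primary outcome, the sample size or any other analysis. It affects how far the comments on adaptations and remote delivery can be trusted, from at most four clients.

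Two assumptions matter. First, the researcher in the table row is taken to be the student researcher/therapist, as the sections on study management and risk indicate. Second, the interview schedule has not been seen; if it already asks about adaptations, all that remains is to name it as a source and to report where support comes from.

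**What to change.** 1. Add to the Change Interview an open question on how the therapy was adjusted for the client, followed by a neutral prompt on which adaptations, including telephone or videocall delivery, helped, hindered or made no difference.
2. Include the answers in the Framework Analysis already planned for that interview.
3. Name the Change Interview and the HAT as sources in the adaptations row of the Table of Outcomes.
4. In the session-content notes already planned, record the session at which each adaptation began, so that it can be marked on the PQ and ORS plots.
5. In the write-up, state for each adaptation whether support comes from the client, the therapist or both. Client endorsement should not be the sole test: it would replace several sources with one retrospective self-report.

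The cost is a slightly longer interview and one more entry in the notes. Prompts carry some risk of agreeable answers, which is why the open question comes first. Fewer adaptations may end up reported as supported. Sample size, treatment and the other analyses do not change.

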If the study is terminated prematurely the CI will notify the REC, including the reasons for premature termination.

PEER REVIEW

As part of the requirements for the DClinPsy course, this research has been through a number of stages in order to check it meets scientific quality. Two academic research staff, one from the University of Nottingham and one from the University of Lincoln, have formally reviewed the project protocol. The outcome was that it is of pass standard, feasible and of clinical importance. Progress since submission of the protocol to the course (May 2019) was assessed at the Research Annual Review (October 2019), where it was agreed that the research was progressing to the sufficient level. Prior to submission for IRAS approval for the study has also been sought from the Sponsor of the research (University of Lincoln) and Trust R&D where the research will take place (Nottinghamshire Healthcare NHS Foundation Trust). IRAS will also involve review by a REC panel. Once the study has finished, the same academic research staff will mark the Thesis before submission of journal article to a peer-reviewed journal. This study will also be supported by the research team to ensure academic quality.

PUBLIC & PATIENT INVOLVEMENT

Participants will be provided a summary of the main findings from the study, should they request this when asked at the end of the study. A summary of the findings will also be presented to the Mental Health Service for Older People (MHSOP), where the study will be carried out. As the project is part of a Doctoral Thesis, a manuscript of the thesis will be stored on the University of Lincoln Repository, along with any journal articles that result from the study.

PROTOCOL COMPLIANCE

Accidental protocol deviations may occur at any time. Accidental protocol deviations will be adequately documented on the relevant forms and reported to the Chief Investigator and Sponsor immediately.

Therapy will use the ACT treatment protocol suggested by Petkus and Wetherell (2013), detailed above. However, this is only a guideline and may be adapted based on participant factors. As ACT is a processes-based therapy, rather than a single manualised procedural treatment, adherence to a strict protocol is not theoretically mandated (Hayes & Hoffmann, 2017). Hayes & Hoffmann, 2017). Content of all sessions will be noted so that later process-change analyses can be performed.

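### Table 1, area 2 describes a content match but tests it only by correlating the HAT with scores, which cannot show such a match and may reuse the HAT-SPQ comparison of area 5

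*Combined protocol and SAP*

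**What the plan says.** All references are to the combined protocol and SAP.

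- **Area 2, description (Data Analysis, Table 1, row 2):** "Content of post-therapy changes correspond to specific processes within therapy".
- **Area 2, method (same row):** "Correlations between within therapy measures (HAT), and quantitative outcome measures", by Pearson or Spearman. The outcome measures are not named.
- **Area 5 (Table 1, row 5):** the idea is one of timing, "Important events precede stable shifts in client problems". The method is "Correspondence between within therapy measure (HAT) and variation in" the client's problem as scored on the SPQ, by Pearson or Spearman correlation and visual analysis.
- **Two-area rule (Study Design, Affirmative brief):** there are five areas, "with evidence in at least two areas required to warrant adjudication". Nothing says that the areas must rest on different data.
- **Timing (Table of Outcomes):** the HAT and ORS are completed at the end of every session and the PQ/SPQ before every session. The OPQOL-brief, HADS and CompACT-8 are taken at "Baselines, pre-, mid- and post-intervention, and at six-week follow up".
- **Status of the measures (Secondary Outcomes):** the PQ/SPQ is listed as a change measure. The HAT is described as qualitative, and no scoring rule is given.
- **Session records (Protocol Compliance):** "Content of all sessions will be noted so that later process-change analyses can be performed".

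**The concern.** The description and the method of area 2 ask different questions. The description is about content: does this particular change correspond to that particular piece of work? The method asks whether two series of numbers move together. A high coefficient would not identify the change or the process, and a low one would not rule out a match.

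The method also leaves the choice of score open. The student researcher/therapist delivers the therapy, completes the HAT with the client and runs the analyses. The schedule favours weekly scores, because the main scales meet the HAT so rarely. If the SPQ is chosen, areas 2 and 5 can rest on one association, and the brief would present it to the panel as two areas of evidence.

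At stake is the third guiding question under Secondary Objectives: which ACT-specific, non-specific or extra-therapeutic factors contributed to change. Area 2 is the row of Table 1 best placed to tie a named change to a named ACT process, and its method cell does not do so.

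**Working it through.** The plan states no alpha, no threshold for an area being met and no number of pairs, so there is no figure of its own to reproduce here.

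**1. How often the HAT meets each score** (Table of Outcomes, Schedule of Procedures, Study Regimen)

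- HAT: sessions 1 to 12, which are weeks 4 to 15.
- OPQOL-brief, HADS, CompACT-8: weeks 1, 2, 3, 4, 9, 15 and 20.
- Overlap: weeks 4, 9 and 15 (sessions 1, 6 and 12), so **3 pairs**. Baseline 4 falls on the day of session 1 only ideally. If it does not, **2 pairs** remain, and two points always give r = +1 or -1 unless there is a tie.
- HAT with ORS: up to 12 pairs.
- HAT with same-session SPQ: up to 12 pairs. HAT with the next session's SPQ: up to 11, or 12 if the PQ repeated within the final session is set against that session's HAT.
- The SRS is also weekly, but it measures alliance.

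**2. What so few pairs can show**

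The critical Pearson coefficient at two-sided 5% (an assumed level) is r = t / sqrt(n - 2 + t²), with t the 97.5% point on n - 2 degrees of freedom.

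- n = 3: t = 12.706, so r = 12.706 / sqrt(1 + 12.706²) = **0.997**.
- n = 11: t = 2.262, so r = 2.262 / sqrt(9 + 2.262²) = **0.602**.
- n = 12: t = 2.228, so r = 2.228 / sqrt(10 + 2.228²) = **0.576**.
- Spearman, n = 3: 3! = 6 orderings, of which 2 give |rho| = 1, so the smallest two-sided p is 2/6 = **0.33**.

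**3. Whether one result can serve two areas**

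Row 2 accepts any quantitative outcome measure, and the SPQ is a listed outcome. Row 5 uses the HAT against the SPQ. A HAT-SPQ correlation therefore fits the wording of both rows.

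**4. Illustration of the two-area rule** (assumed: 5% chance of a spurious positive per area, areas otherwise independent)

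- Five separate areas: P(at least 2) = 1 - 0.95^5 - 5 × 0.05 × 0.95^4 = **2.3%**.
- Areas 2 and 5 are one association counted twice: 0.05 + 0.95 × P(at least 2 of 3) = 0.05 + 0.95 × 0.00725 = **5.7%**.
- Only the four correlation-based areas (2 to 5): 1.4% if separate. If 2 and 5 are one association, 0.05 + 0.95 × 0.05² = 5.2%. If 2 and 5 count once, 0.7%.

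**5. If area 2 uses the same session and area 5 the next session**

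Two unrelated weekly series of 12 points were simulated (first-order autocorrelation, 40,000 runs per value, 5% Pearson tests). Both comparisons came out significant in 0.2% of runs with no autocorrelation, 0.6% at 0.3, 3.9% at 0.6 and 10.2% at 0.8. The autocorrelation values are assumed.

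**The case against.** The strongest reply is that Table 1 itself suggests a narrower meaning of outcome measures. Row 3 calls the SPQ the change questionnaire and row 5 treats it as the client's problem. Row 4 speaks of outcome measures from baseline onwards, where no PQ is taken. On that reading rows 2 and 5 use different scores and nothing is counted twice. This reading is possible, but it leaves area 2 with three pairs at most and still without a content match.

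Other parts of the reply stand:

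- The overlap is not forced even on the broad reading, because the ORS is also weekly.
- Row 5 implies a lag, since the PQ precedes each session and the HAT follows it, and it adds visual analysis. The two rows need not be the same calculation, although no lag is written down.
- A reader might infer that the false-positive rate for a case rises from 2.3% to 5.7%. The documents do not support this as an estimate. They set no threshold, area 1 is a Framework Analysis of an interview, and areas 3 and 5 both use the SPQ, so independence is itself doubtful.
- A reader might also infer that passing the two-area rule is a finding for ACT. It is not. The sceptic brief, with reliable change and checks for statistical artefacts, and a panel of three still follow.
- Nor is content linkage absent from the study. The case records cross-reference the Change Interview, process notes and recordings, session content is noted for process-change analysis, and the panel attributes change to types of factor. The gap is in the method cell of area 2.

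**Conclusion.** The point holds in a limited form. The method for area 2 does not test what area 2 describes. This follows from the wording alone and needs no assumption. For the primary outcome, the HADS and the CompACT-8, the stated correlation has three pairs at most (two if Baseline 4 is on another day) and is uninformative within a case. The figures of 0.997 and 0.33 assume a two-sided 5% test, but three points say little under any criterion.

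Double use of a HAT-SPQ association across areas 2 and 5 is allowed by the text but not required by it. Its effect cannot be sized from the documents. The percentages above show direction only, and 5.7% is the full-overlap case. The consequence is bounded because the rule only opens adjudication, but the panel works from the briefs, so one association presented as two would reach it in that form.

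This should be settled before the briefs are written. The absence of a HAT scoring rule is a separate gap. It affects both rows as written.

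**What to change.** 1. **Area 2 method.** Replace the correlation with a content mapping. List each post-therapy change from the SPQ items (including any re-authored at the final session) and from the changes named in the Change Interview. Map each to the session content notes, the HAT text and the ACT area worked on. Rate the match on a scale fixed in advance: none, general or specific. Leave the client's own attribution of change in area 1, so that the interview does not supply the same evidence twice.
2. **Area 5 method.** Keep the HAT-SPQ comparison here only, and set the HAT against the next session's SPQ so that the event precedes the shift.
3. **Two-area rule.** Add that areas resting on the same association, or on the same Change Interview statement, count once.

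The cost is wording in Table 1 and in the affirmative-brief paragraph, plus a few hours of mapping per case. The SPQ, HAT, session notes and Change Interview are already planned, so participants carry no extra burden. The downside is that slightly fewer areas can be claimed.
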